RSD	Reflex Sympathetic Dystrophy
SADE	Serious Adverse Device Effect
SAE	Serious Adverse Event
SAP	Statistical Analysis Plan
SCS	Spinal Cord Stimulation
V	Volts

Intellis, AdaptiveStim, Restore, RestoreUltra, RestoreAdvanced, RestoreSensor, SureScan, and Vanta are trademarks of Medtronic.

MDT18036 Version 3.0 Page 9 of 66

3. Synopsis

Title	Spinal Cord Stimulation (SCS) Research Study	
Clinical Study Type	Post-market	
Product Name	Medtronic Implantable Neurostimulation Systems	
Sponsor	Medtronic, Inc.	
	[name]	
	[name]	
	U.S.A.	
	[contact]	
Indication under	Approved indication of spinal cord stimulation as an aid in the	
investigation	management of chronic, intractable pain of the trunk and/or limbs.	
Investigation Purpose	To characterize the effects of stimulation parameters on pain relief	
	and other cohort specific outcomes.	
Product Status	All devices used in this study are commercially available and will be	
	used within the intended approved indication.	
Primary Objective	To characterize the pain scores, specific to the indication associated	
	with SCS implant, with different SCS parameters.	
	•	
	-	
	•	
Study Design	This is a prospective, multi-center, post-market study to characterize	
Study Design	the effects of stimulation parameters on pain relief,	
	It is estimated that up to 360	
	subjects will be enrolled in the United States.	
	subjects will be emolied	
	The overall study duration, from first subject enrollment to last	
	subject visit, is expected to last approximately 10 years. Multiple on-	
	label stimulation parameters will be studied throughout the execution	
	of this clinical investigational plan.	
	or this chilical investigational plan.	

	study cohort is defined as a group of subjects who share the same recommended programming parameters and follow-up visit cadence. The longer enrollment period enables the research of SCS parameters over time as the science and technology in SCS develops. he completion of the study is defined as the approval of the Final Clinical Study Report and closure of all sites.	
Sample Size	It is estimated that up to 360 subjects will be enrolled. Considering the research interests in multiple stimulation settings and longer enrollment of the study, a sample size of up to 360 subjects is deemed to be reasonable to characterize the effects of changes to stimulation settings, as well as to provide data for consideration of future studies. The sample size for each on-label programming parameter group may vary based on the research interest.	
Inclusion/Exclusion Criteria	Inclusion Criteria: To be included in this study, a patient must meet the following inclusion criteria: 1. 22 years of age or older 2. Implanted with a Medtronic neurostimulation system, for a labeled indication, and expected longevity of neurostimulator is at least 16 months 3. Willing and able to provide signed and dated informed consent 4. Capable of comprehending and consenting in English 5. Willing and able to comply with all study procedures and visits 6. Able to differentiate between pain associated with the indication for SCS implant and other types of pain, as determined by the investigator, or designee	
	Exclusion Criteria: To be included in this study, a patient must not meet any of the following exclusion criteria:	

MDT18036 Version 3.0 Page 11 of 66

	 Implanted with neurostimulation system for an off-label indication Currently enrolled or planning to enroll in an interventional clinical study that could potentially confound the study results (co-enrollment in an interventional study is only allowed when documented pre-approval is obtained from the Medtronic study manager, or designee) If female, pregnant or is of child-bearing potential and unwilling to use a medically acceptable form of birth control during the study Has untreated major psychiatric comorbidity, as determined by the investigator, or designee Has a non-rechargeable neurostimulator where the battery longevity is not able to be estimated with the battery longevity calculator 	
Study Procedures and	Upon obtaining informed consent, each subject will complete an	
Assessments	Upon obtaining informed consent, each subject will complete an Enrollment Visit The following measures may be used during the study:	
Safety Assessments	Subjects will be assessed from enrollment through the end of the	
_	study for adverse events related to the following:	
	The SCS system and accessories (device-related)	
	SCS therapy (therapy-related)	
	SCS procedure (procedure-related)	
	·	
	In addition, all device deficiencies reported during the study will be collected.	

MDT18036 Version 3.0 Page 12 of 66

Descriptive statistics will be reported for the primary objectives. In addition, the statistical approach may vary based on the research question to be addressed in each cohort Where applicable, hypothesis testing may be performed to characterize change from baseline. Hypothesis testing may not be performed on all cohorts. Sample sizes in cohorts with hypothesis testing will be estimated based on at least 80% power with a significance level of 0.05 for two-sided tests or 0.025 for one-sided tests. Sample sizes in cohorts with no hypothesis testing may vary depending on the research questions to be addressed. Device, procedure, and therapy related adverse events and device deficiencies will be presented in summary tables.

4. Introduction

This post-market clinical study will be conducted with up to 40 sites and include subjects treated with SCS, consistent with FDA approved indications and instructions for use, using programming parameters within the capabilities of approved SCS devices. It is estimated that up to 360 subjects will be enrolled.

The study will be conducted in accordance with this protocol, the ethical principles that have their origin in the Declaration of Helsinki, all applicable regulatory requirements (21 Code of Federal Regulations (CFR) §11 Electronic records; electronic signatures, 21 CFR §50 Protection of human subjects, 21 CFR§54 Financial disclosure by clinical investigators, 21 CFR §56 Institutional review boards, and 21 CFR §803 Medical device reporting), and will comply with Good Clinical Practices (GCP) as guidelines for this study.

4.1 Background

Spinal cord stimulation (SCS) has been proven to be an effective therapy for pain relief. Three parameters are programmed to deliver stimulation in SCS systems: pulse width (μ s), frequency (Hz), and amplitude (mA or V). Pulse width determines the number of neurons targeted for therapy; while

Medtronic Business Restricted

frequency affects the quality or feeling of the neurostimulation. Amplitude controls the stimulation intensity and may be adjusted above or below sensory perception thresholds. Most clinical trials are conducted using a range of parameters rather than a specific parameter set; therefore, no conclusions can be made about specific parameters.

Pulse width is the duration of each electric impulse in microseconds. As the duration of the stimulus increases, an increase in the recruitment of nerve fibers occurs. Limited clinical research has been conducted on pulse width optimization in SCS. In one single-blinded, prospective study, Yearwood et al. (2010) surveyed pulse widths from 50 to 1000 µs in 19 back pain subjects. Approximately 37% of subjects selected to increase their pulse width values as compared to their original program and the median pulse width of all final programs was 400 µs. Abejon et al. (2015) conducted a clinical study examining 46 subjects programmed at a fixed frequency of 50 Hz and pulse widths between 50 - 1000 μs. Subjects achieved the best degree of satisfaction at pulse width 331.27+/- 227 μs and were dissatisfied at pulse widths exceeding 700 µs. Subjects preferred pulse widths ranging from 320-500 µs which agrees with the Yearwood study for support of longer pulse widths within the conventional range.2

Frequency or rate of stimulation is a parameter that may be modulated to produce different analgesic outcomes.3 While the range of frequencies for most rechargeable implantable SCS devices (e.g., Medtronic RestoreSensor) is 2 – 1200 Hz, the conventional stimulation frequencies range from 50 to 120 Hz. 4 Since 2010, there has been a focus on using higher frequencies (1000 Hz -10 kHz) for stimulation; for which, there are publications reporting significant pain relief. 5,6 Several small studies have explored the upper limits of conventional SCS frequencies, 1000- 1200 Hz, and have reported that subjects who have lost pain relief from conventional SCS at lower frequencies could have pain relief restored at these

Studies have tested sub-perception stimulation amplitudes, but maintained traditional frequency ranges (60-85 Hz) and pulse widths (210-390 µsec) in small groups of subjects or case reports. ^{11, 12, 13} In one small case series of neuropathic pain, parameters set at conventional frequency and pulse width settings at sub-perception amplitudes relieved neuropathic pain better than no stimulation but were less effective than supra-threshold stimulation. Recently, new programming algorithms claim to be effective at sub-perception amplitudes, but these algorithms include high frequencies 14, 15, 16 or long pulse widths. ^{17, 18} To date, there are no studies with a focus on surveying the range of amplitudes.

In addition, the recent studies evaluated various 'cycling' or 'pulsing' techniques wherein the stimulation paradigms are cycled on and off for specific times to improve battery longevity for non-rechargeable devices and time between recharges for rechargeable devices. This promising new approach has yet to be well characterized or understood as to which cycling parameters are the most efficacious. In conclusion, neurostimulators have the ability to stimulate in a wide range of on-label parameter settings; however, more can be understood about the effects of these parameters on patient pain relief or physiologic processes that are ultimately related to patient benefits. This study explores the on-label parameters to determine these effects.

⁷ Smith H1, Youn Y, Pilitsis JG. Successful use of high-frequency spinal cord stimulation following traditional treatment failure. Stereotact Funct Neurosurg. 2015;93(3):190-3. doi: 10.1159/000380825. Epub 2015 Apr 1.

⁸ North JM1, Hong KJ2, Cho PY3. Clinical Outcomes of 1 kHz Subperception Spinal Cord Stimulation in Implanted Patients With Failed Paresthesia-Based Stimulation: Results of a Prospective Randomized Controlled Trial. Neuromodulation. 2016 Oct;19(7):731-737. doi: 10.1111/ner.12441. Epub 2016 May 17.

⁹ Youn Y1, Smith H, Morris B, Argoff C, Pilitsis JG. The Effect of High-Frequency Stimulation on Sensory Thresholds in Chronic Pain Patients. Stereotact Funct Neurosurg. 2015;93(5):355-9. doi: 10.1159/000438998. Epub 2015 Oct 8.

4.2 Purpose

Medtronic, Inc. is sponsoring the SCS Research Study, a prospective, multi-center, post-market clinical study. The purpose of this study is to characterize the effects of stimulation parameters on pain relief

5. Objectives and/or Endpoints

²² Turner JA, Loeser JD, Deyo RA, Snaders SB. Spinal cord stimulation for patients with failed back surgery syndrome or complex regional pain syndrome: a systematic review of effectiveness and complications. Pain. 2004 Mar; 108(1-2):137-47.

²⁵ Duarte RV, Andronis L, Lenders MW, de Vos CC. Quality of life increases in patients with painful diabetic neuropathy following treatment with spinal cord stimulation. Qual Life Res. 2016 Jul;25(7):1771-7. doi: 10.1007/s11136-015-1211-4.

MDT18036 Version 3.0 Page 17 of 66

Most clinical studies reporting on the pain-relieving effects of SCS are observational case studies with no appropriate comparator or systematic reviews of the aforementioned. There are prospective studies that demonstrate at least 50% pain relief or improvement in function in 60% of CRPS patients implanted with SCS systems ^{24, 25, 26, 27, 28}, 50 to 60% of FBSS patients. ^{29,30,31, 28} and 50-63% in Painful Diabetic Peripheral Neuropathy patients.²³ However, a number of clinical reviews report that the pain-relieving effect of SCS can diminish over time.³² While there is a deficiency of multiple evidence-based studies demonstrating efficacy of long term SCS, there are even fewer studies that provide sufficient data regarding SCS parameter effects (eg, frequencies, pulse widths, cycling duties, etc.) on clinical outcomes along with long term effects. Research studies are needed to address the gap in our knowledge of SCS parameters and how they differentially, but effectively, modulate central nervous system mechanisms that drive chronic intractable pain, the underlying causes, or relief from pain.

Product Description 7.

7.2 Manufacturer

MDT18036

The neurostimulation systems are manufactured by Medtronic, Inc. with operational headquarters in [name].

7.4 Product Return

All products are commercially available, and no products related to the neurostimulation system will be provided from Medtronic as a part of this study.

When explanting a device (e.g., replacement, cessation of therapy, or postmortem), or when disposing of accessories, if possible, return the explanted device with completed paperwork to Medtronic for analysis and disposal. To allow for device analysis, do not autoclave the device or expose the device to ultrasonic cleaners. Dispose of any unreturned components according to local environmental regulations.

7.5 Product Accountability

No product accountability is required for the study. All products are considered commercially available, and Medtronic will not be providing products related to the neurostimulation system for this study.

MDT18036 Version 3.0 Page 19 of 66

Subjects who participate in the study may be asked to surrender their patient programmer to site personnel for follow-up periods (for example, if a subject is implanted with a neurostimulator that can be turned off using a recharger and does not require a patient programmer for recharging).

Site personnel will store each subject's patient programmer in a secure location. Each subject will be given back their patient programmer prior to the end of their participation in the study.

Study Site Requirements

Investigator/Investigation Site Selection 8.1

The role of the principal investigator is to implement and manage the day-to-day conduct of the clinical investigation as well as ensure data integrity and the rights, safety and well-being of the subjects involved in the clinical investigation.

The principal investigator shall:

- Be qualified by education, training, and experience to assume responsibility for the proper conduct of the clinical investigation
- Be experienced in the field of application and training in the use of spinal cord stimulation
- Be able to demonstrate that the proposed investigational study site:
 - Has the required number of eligible subjects needed within the recruitment period
 - Has one or more qualified investigators, a qualified investigational study site team, and adequate facilities for the foreseen duration of the clinical investigation

Study site personnel qualification and training will be completed and documented prior to participation in this study.

8.2 Study Site Activation

During the site activation process (prior to subject enrollment), Medtronic will train study site personnel on the clinical investigation plan (CIP), relevant standards and regulations (as required), informed consent (IC), programming, and data collection and reporting tools. If new members join the study site team, they will receive training on the applicable study requirements relevant to their role before contributing to the study.

Prior to performing study related activities, all regulatory requirements shall be fulfilled, including, but not limited to the following:

- IRB approval (and voting list, as required by local law) of the current version of the CIP and
- Fully executed Clinical Trial Agreement (CTA)

MDT18036 Version 3.0 Page 20 of 66

- CV/medical license of investigators and key members of the investigation study site team (as required).
- Documentation of delegated tasks.
- Documentation of study training.

In addition, all participating study site staff must be trained on the current version of the CIP as well as on the applicable study requirements depending on their role and must be delegated by the principal investigator to perform study-related activities.

Medtronic will provide each study site with documentation of study site/investigator readiness; this letter must be received prior to performing study-related activities.

8.3 **Role of the Sponsor Representatives**

In addition to performing monitoring and auditing activities, qualified and trained sponsor representatives may provide support at the study site as required for the study under supervision of the Principal Investigator, including:

 Provide study training relevant and pertinent to the involvement of personnel conducting study activities and investigator responsibilities

These activities will be performed under the supervision of the investigator, or appropriately delegated study personnel, and will not bias the outcome of study, affect the quality of research data, or compromise the rights and welfare of human subjects. Any data collection completed by Medtronic personnel will be clearly identified as such.

Selection of Subjects

Study Population 9.1

A Medtronic implantable neurostimulation system is indicated for spinal cord stimulation (SCS) as an aid in the management of chronic, intractable pain of the trunk and/or limbs including all conditions approved by the FDA at the time of initiation of any individual cohort.

This study will enroll a sub-set of the population indicated for SCS systems. Subjects who meet the eligibility criteria listed in Sections 9.3-9.4 are eligible to be enrolled in the study.

MDT18036 Version 3.0 Page 21 of 66

9.2 Subject Enrollment

When a subject and the principal investigator or authorized designee, as required, have personally signed and dated the IC, the subject is considered enrolled in the study. The date the subject signed the IC must be documented in the subject's medical records.

Subjects will be screened to ensure they meet all of the inclusion and none of the exclusion criteria prior to being eligible to participate in the study. Subjects may be enrolled in multiple cohorts to test different on-label programming parameter groups.

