Subjects are considered enrolled at the time the study specific ICF is signed. If a subject enrolls for participation in multiple cohorts, a new consent form will be signed for each subsequent cohort. Informed consent must be obtained from the subject prior to initiation of any study-specific procedures. Subjects must be able to personally sign and date the consent form to participate in this study. Signing and dating of the ICF or HIPAA authorization or other data protection form by a legally authorized representative will not be permitted for this study. Subjects will be required to sign and date a HIPAA authorization or other data protection form as required by local regulations before participating sites can collect, use and submit subject information to the study sponsor. The Consent Form and Authorization to Use and Disclose Personal Health Information/ Research Authorization/other legally required privacy language must be given to the subject in a language he/she is able to read and understand. Only subjects capable of reading and understanding English are eligible to participate in this study.

If the informed consent form is obtained the same day the subject begins participating in study-related procedures, it will be documented in the subject's case history that consent was obtained prior to participation in any study-related procedures.

The original signed ICF must be filed in the hospital/clinical chart and/or with the subject's study documents. A copy of the informed consent form and signed Authorization to Use and Disclose Personal

MDT18036 Version 3.0 Page 27 of 66

Health Information/Research Authorization/other legally required privacy language must be provided to the subject.

[figure not shown]
The informed consent form and Authorization to Use and Disclose Personal Health Information/Research Authorization/other legally required privacy language must be available for monitoring and auditing.

Any changes to a previously approved informed consent form throughout the course of the study must be submitted and approved by Medtronic and the IRB reviewing the application before being used to consent a prospective study subject. The document(s) must be controlled (i.e. versioned and dated) to ensure it is clear which version(s) were approved by the IRB.

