16.4 Confidentiality

All records and other information about subjects participating in this clinical study will be treated as confidential. Subject confidentiality will be maintained throughout the clinical study to the extent permitted by law. That is, every attempt will be made to remove subject identifiers from clinical study documents. For this purpose, a unique subject identification code (study - site - subject number) will be assigned and used to allow identification of all data reported for each subject. This will also ensure that the information can be tracked back to the source data.

Study data may be made available to third parties, e.g., in the case of an audit or inspection performed by regulatory authorities, provided the data are treated confidentially and that the subject's privacy is guaranteed. The identity of a subject will never be disclosed if study data are published. Only anonymized data will be analyzed and published.

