4.1 Primary Objectives

To characterize the pain scores, specific to the indication associated with SCS implant, with different SCS parameters, at enrollment and during follow-up periods.

5. Investigation Plan

This is a prospective, multi-center, post-market study to characterize the effects of stimulation

SCS Research Statistical Analysis Plan				Form
	Revision 3.0	Page 5 of 12		Medtronic
parameters on pain relief be enrolled	in the United States.	. It is estimated that up	to 360	subjects will

The overall study duration, from first subject enrollment to last subject visit, is expected to last approximately 10 years.

Multiple on-label stimulation parameters will be studied throughout the execution of this clinical investigational plan A study cohort is defined as a group of subjects who share the same recommended programming parameters

The longer enrollment period enables the research of SCS parameters over time as the science and technology in SCS develops.

The completion of the study is defined as the approval of the Final Clinical Study Report and closure of all sites.

This document is electronically controlled

CONFIDENTIAL

Medtronic Business Restricted 056-F286, Statistical Analysis Plan Template Rev C

Determination of Sample Size 6.

It is estimated that up to 360 subjects will be enrolled. Considering the research interests of multiple stimulation settings and longer enrollment of the study, a sample size of up to 360 subjects is deemed to be reasonable to characterize the effects of changes to stimulation settings, as well as to provide data for consideration of future studies.

The sample size for each stimulation setting may vary based on the research interests. Table 1 shows precision estimates (the distance from mean to limits) by sample size and standard deviation of . A sample size of 30 produces a two-sided 95% confidence interval with the precision that is equal to 0.93 when the estimated standard deviation is 2.5.

Sample size		Standard deviation (S)			
(N)	1.0	1.5	2.0	2.5	3.0
10	0.72	1.07	1.43	1.79	2.15
15	0.55	0.83	1.11	1.38	1.66
20	0.47	0.70	0.94	1.17	1.40
30	0.37	0.56	0.75	0.93	1.12
40	0.32	0.48	0.64	0.80	0.96

7. Statistical Methods

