7.2 General Methodology

Data analysis will be performed by Medtronic-employed statisticians or designees. A validated statistical software package (eg, SAS version 9.4 or higher) will be used for all analyses. Summary statistics will be presented for continuous measures (N, mean, median, standard deviation, minimum and maximum) and categorical measures (N, percent, frequency distributions) with two-sided 95% confidence intervals as appropriate. Further analysis details are provided in section 7.9.

This SAP describes the statistical methods that might be used in the analyses

. These are general methodologies.

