7.3 Center Pooling

The investigators of this study will conduct the study according to a common protocol and use the same CRFs to collect study data. The site study personnel will be trained prior to the study initiation at each site. Periodic study monitoring by Medtronic will ensure compliance with protocol requirements. There is no a priori provision to exclude any sites from the analysis. The data from sites will be pooled for analysis. To reduce the possibility of atypical results from a site overly influencing the combined results, no more than 90 subjects will be enrolled at each site.

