7.9.1 Primary Objective

Objective

To characterize the pain scores specific to the indication associated with SCS implant with different SCS parameters at enrollment and during follow-up periods.

Hypothesis

There is no hypothesis testing for the primary objective. The purpose of the primary objective is to characterize the pain scores by different stimulation parameter groups during follow-up periods.

Experimental design

an average overall	pain score is calculated		
		pain scores,	

Analysis method

The mean and standard deviation as well as median, min, max of the pain scores will be summarized at follow-up visits. Pain scores may also be summarized by different stimulation parameter groups. Subjects who provide data will be included in the analysis.

This document is electronically controlled

CONFIDENTIAL

This document is electronically controlled

CONFIDENTIAL

Medtronic Business Restricted 056-F286, Statistical Analysis Plan Template Rev C

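### Must the plan say whether the 360 total and the 90-per-site cap count persons or enrolments, given that one person may join several cohorts?

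*Protocol*

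**What the plan says.** Protocol 9.2 allows repeat participation: "Subjects may be enrolled in multiple cohorts to test different on-label programming parameter groups". Protocol 10.6 fixes the moment of enrolment, "Subjects are considered enrolled at the time the study specific ICF is signed", and adds "If a subject enrolls for participation in multiple cohorts, a new consent form will be signed for each subsequent cohort".

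Both documents estimate a total of up to 360 subjects (Protocol 14.6, SAP section 6). SAP 7.3 sets the site cap and gives the reason for it, which is to keep an atypical site from overly "influencing the combined results, no more than 90 subjects will be enrolled at each site".

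On identity, Protocol 16.4 says that "a unique subject identification code (study - site - subject number) will be assigned". The same sentence goes on to give the purpose, which is to identify all the data reported for each subject.

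On the unit of analysis, SAP section 5 says "A study cohort is defined as a group of subjects who share the same recommended programming parameters"; the Protocol synopsis adds a shared schedule of follow-up visits to that definition. SAP 7.9.1 says that "the pain scores will be summarized at follow-up visits. Pain scores may also be summarized by different stimulation parameter groups". SAP 7.2 provides summary statistics "with two-sided 95% confidence intervals as appropriate". Protocol 14.1 foresees a separate SAP and a final report for each cohort, and Protocol 14.2 times the reports by cohort. Protocol 14.5 permits some high-level descriptive safety summaries across cohorts, if applicable.

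**The concern.** Enrolment is tied to a signature, and the signature is repeated for each cohort. Read literally, a person in two cohorts has enrolled twice. The total and the site cap are both stated as numbers enrolled, so each could be counted in either unit. Protocol 16.4 does not say in terms that the code is kept when a person enters a second cohort.

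Three things could then go wrong:

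- The size of the study and the share that one site may supply would be ambiguous.
- A safety percentage taken across cohorts would be diluted if persons with an event were divided by enrolments.
- A pain mean pooled across cohorts, with an interval that treats every record as independent, would look more precise than it is.

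Two places in the SAP seem to make such pooling likely. The cap of 90 protects combined results and is larger than any group size in the precision table (10 to 40). The wording of SAP 7.9.1 makes the visit summary firm and the summary by parameter group optional.

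**Working it through.** **The plan's own figure.** Inputs from Protocol 14.6 and SAP section 6: n = 30, SD = 2.5, two-sided 95%. Half-width = t(0.975, 29) × 2.5/√30 = 0.934, which rounds to the stated 0.93. All 25 cells of the precision table reproduce with the t quantile. The formula needs n independent persons within one cohort. Someone in two cohorts still appears once in each, so the table stands. The 360 has no formula behind it; the documents call it an estimate and reasonable.

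**What the counting unit would change.** The documents give no overlap rate. Assume that a share f of persons joins exactly two cohorts.

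| Quantity | Formula | f = 0.10 | f = 0.25 | f = 0.50 |
|---|---|---|---|---|
| Persons, if 360 counts enrolments | 360/(1+f) | 327 | 288 | 240 |
| Cohort places, if 360 counts persons | 360(1+f) | 396 | 450 | 540 |
| One site's share, if 90 counts persons and 360 counts enrolments | 90(1+f)/360 | 27.5% | 31.3% | 37.5% |
| A 10% event rate per person, divided by enrolments | 10%/(1+f) | 9.1% | 8.0% | 6.7% |

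The first two rows change a headcount on which no precision or power statement depends. The third needs the same noun to mean persons in SAP 7.3 and enrolments in SAP section 6; with one unit for both, 90/360 = 25%. The fourth needs persons in the numerator, enrolments in the denominator, and no one counted in both of their enrolments. SAP 7.10 already reports the number and percentage of subjects with at least one event, which is a count of persons.

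**Which unit the text supports.** Protocol 9.2 separates being enrolled in the study from being enrolled in several cohorts, and it uses subject for the person who does the latter. The code in Protocol 16.4 is made of study, site and subject number. Nothing in it refers to a cohort, and its stated use is to hold together all data for a subject. This supports one code per person.

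**Whether pain results are pooled across cohorts.**

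- SAP 7.3 is headed Center Pooling, and its preceding sentence pools data from sites. The combined results are therefore naturally results combined over sites, as in Protocol 14.1.
- SAP 7.9.1 also states, under Hypothesis, that the purpose of the primary objective is to describe pain by stimulation parameter group. The optional wording under Analysis method cannot be read without that sentence.
- Under the synopsis definition, cohorts can differ in visit schedule, so a mean by visit across cohorts has no evident common time axis.
- The primary analysis in SAP 7.9.1 lists mean, SD, median, minimum and maximum, with no test and no interval. Intervals enter only through the general clause in SAP 7.2.

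No visible text plans a pooled pain estimate with an interval, so there is no such interval to correct.

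**The case for a change.** The strongest reply is that these are study-level matters. The file holds the overall SAP, and a rule that crosses cohorts would sit awkwardly in a SAP written for one of them. The cap is 25% of 360, a whole-study quantity, and it could hardly bind in a cohort of 40. Protocol 14.5 does allow safety summaries across cohorts. Over about 10 years of rolling enrolment, it is easier to keep one identifier per person from the start than to link people afterwards.

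Part of this stands. No visible sentence defines the unit outright, and none says in terms that the code carries over. A cross-cohort safety table is possible.

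The rest does not carry the point. The sizes of 10 to 40 are illustrative; Protocol 14.6 lets group size vary and sizes any hypothesis-testing cohort by power. A cap that seldom binds within a cohort limits a site's share of the study, but it does not show that pain scores are averaged over cohorts. A cross-cohort safety table would be descriptive and, under SAP 7.10, would count subjects. Text is also blacked out beside the enrolment total and around the cohort definition, and the cohort-specific SAPs are not in the file, so silence in the visible text cannot be taken as silence in the plan.

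**Conclusion.** No change is needed. What is missing is an explicit statement that subjects means unique persons. That is the plain reading, and it fits the structure of the subject code and the way adverse events are tabulated. An analyst following the plan would adopt it and reach sound results.

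The effect on the planned cohort reports is nil: the half-width of 0.93 and the single-cohort summaries do not depend on the counting unit. Outside those reports, the total could differ by the headcounts above (327 to 240 persons, or 396 to 540 places). The site share and the safety percentage would move only if units were mixed in a way the text does not suggest. All these ranges rest on an assumed 10% to 50% of persons joining two cohorts. The conclusion assumes that each person enters a given cohort once and that reporting stays by cohort, as Protocol 14.1 and 14.2 describe.
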